3.2.4 Follow-up 1/Dispensing 2 visit

Subjects should attend wearing the study lenses which should have been in situ for at least two hours. Subjects who attend without lenses in situ for at least two hours will usually be rescheduled.

The following procedures will be performed (any ocular measurement procedures outlined below will be carried out on each eye):

1. Any medical or ocular issues since the last visit will be recorded.
2. Lens wearing times since the previous visit will be recorded (hours per day, days per week and comfortable hours per day).
3. Lens wearing time on study visit day.
4. The subject will be asked about their agreement with statements related to lens comfort [REDACTED]
5. [REDACTED]
6. The subject will be asked to score the following with reference to appropriate

- Ease of lens removal

7. [REDACTED]

8. Retrieval of any unused lenses.

9. [REDACTED]

10. [REDACTED]

11. Lens fit, toric lens fit, rotational recovery [REDACTED], as described in section 3.2.2 above.

12. The lenses will then be removed and discarded.

13. [REDACTED]

[REDACTED]

14. The second randomised lens pair will be fitted and allowed to settle for five minutes.

15. The subject will apply the second randomised pair of lenses. Orientation of toric markings do no need to be taken into consideration.

16. Lenses are allowed to settle for five minutes.

17. Toric lens fit will be assessed as described in Section 3.2.2.

18. Rotational recovery will be assessed one minute after manually displacing the lens 30 degrees temporally:

a. [REDACTED]

[REDACTED]

[REDACTED]

[REDACTED]

[REDACTED]

d. A timer begins, the subject while seated at the slit lamp is instructed to look straight ahead and to blink normally.

e. After one minute has elapsed, record the location of the lens marker and record the value on the protractor.

19. Lens fit will then be assessed using the following evaluations: horizontal and vertical centration, corneal coverage and movement, using the grading scales in [REDACTED]

20. Lens deposition and wettability will be graded using the grading scales in [REDACTED]

21. [REDACTED]

22. [REDACTED]

23. [REDACTED]

15. The subject will be issued with 10 pairs of contact lenses for the second study period.

16. The subject will then be discharged and asked to return for the one-week follow-up visit wearing the study lenses for at least two hours. Subjects should be asked to wear their lenses for a minimum of eight hours per day, five days per week.

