1.4 Study outcome measures

The primary outcome measure for this study is subjective handling on lens removal. Secondary measures are lens fit parameters and biomicroscopy scores [REDACTED]

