3.2.3 Dispensing 1 visit

Subjects should attend this visit wearing their spectacles. Subjects attending this visit wearing contact lenses should be rescheduled.

The following procedures will be performed (any ocular measurement procedures outlined below will be carried out on each eye):

1. [REDACTED]
[REDACTED]
2. Any medical or ocular issues since the last visit will be recorded.
3. [REDACTED]
4. The subject will apply the first randomised pair of lenses. Orientation of toric markings do not need to be taken into consideration.
5. Lenses are allowed to settle for five minutes.
6. Toric lens fit will be assessed as described in Section 3.2.2.
7. [REDACTED]
[REDACTED]
[REDACTED]
[REDACTED]
[REDACTED]
[REDACTED]
[REDACTED]
[REDACTED]
[REDACTED]
8. Lens fit will then be assessed using the following evaluations: horizontal and vertical centration, corneal coverage and movement, using the grading scales in
[REDACTED]
9. [REDACTED]
[REDACTED]
10. [REDACTED]
[REDACTED]
[REDACTED]
11. The investigator will confirm that lens fit [REDACTED] are satisfactory:
 - a. In the case of an unacceptable lens fit, proceed to the next randomised lens (on the same day, or as a separate visit).
 - b. In the case of unacceptable vision (less than 6/12), if in the opinion of the investigator an alternate lens from within the available power range would improve vision, then new lenses can be ordered and this visit repeated. If an alternate lens is not indicated then proceed to the next randomised lens (on the same day, or as a separate visit).
12. [REDACTED]
[REDACTED]

13. The subject will be issued with 10 pairs of contact lenses for the first study period.
14. The subject will then be discharged and asked to return for the one-week follow-up visit having worn the study lenses for at least two hours. Subjects should be asked to wear their lenses for a minimum of eight hours per day, five days per week.

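### At Dispensing 2, lens fit and lens surface are graded straight after the lens has been manually rotated 30 degrees, with no written re-settle

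*Combined protocol and SAP*

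**What the plan says.** Section 1.4 gives lens fit the status of a secondary outcome: "Secondary measures are lens fit parameters and biomicroscopy scores". The visible text does not name the visit that supplies it. Section 1.6 states a hypothesis of equality for lens fit and plans non-parametric methods.

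The Dispensing 2 part of section 3.2.4 runs as follows:

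- Step 14: "The second randomised lens pair will be fitted and allowed to settle for five minutes".
- Step 15: "The subject will apply the second randomised pair of lenses". Step 16 gives a further five-minute settle.
- Step 17: toric lens fit.
- Step 18: "Rotational recovery will be assessed one minute after manually displacing the lens 30 degrees temporally". It ends with 18e: "After one minute has elapsed, record the location of the lens marker and record the value on the protractor".
- Step 19: "Lens fit will then be assessed using the following evaluations: horizontal and vertical centration, corneal coverage and movement".
- Step 20: deposition and wettability.

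Section 3.2.3 (Dispensing 1) has one application by the subject (step 4) and one settle (step 5: "Lenses are allowed to settle for five minutes"). Toric fit is step 6, step 7 is blacked out over several lines, and lens fit is step 8, worded as in step 19 above.

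For the follow-up assessment, step 11 of section 3.2.4 lists "Lens fit, toric lens fit, rotational recovery" and refers back to section 3.2.2, much of which is blacked out.

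**The concern.** A test that deliberately moves the lens is placed before grades that are meant to describe how the lens sits and moves on the eye. Reading the marker at one minute makes sense only if the lens may not yet be back at rest. The plan nevertheless moves straight on to centration, coverage and movement.

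This matters for a comparison of lenses because the disturbance need not be equal. The ordering instructions at the end of section 3.2.2 let the axis differ between the two products because they stabilise differently. If they also return at different speeds, each is graded in a different state. Such a difference belongs to the lens and not to the period, so the crossover does not cancel it. A difference in rotational recovery could then appear as a difference in fit.

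A lesser matter is that the second pair is applied and settled in step 14 and again in steps 15 and 16. Sites could time the reading differently.

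**Working it through.** **The plan's own figure.** The plan gives no figure for lens fit. Its only calculation (section 1.6.1) is for ease of removal, with SD 1.5, difference 0.7 and 90% power. Assuming two-sided 5%, n = (1.5 × (1.960 + 1.282) / 0.7)² = 48.2, so 49; the exact paired t calculation gives 51. The stated 50 lies between these, and nothing below changes it.

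**Order at each visit, from the visible text.**

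| Visit | Sequence | Is lens fit graded after displacement? |
|---|---|---|
| Initial (3.2.2) | Lens fit is step 13; the steps just before it are not visible | Cannot be determined |
| Dispensing 1 (3.2.3) | Toric fit (6), blacked out (7), lens fit (8) | Cannot be determined |
| Follow-ups (3.2.4 step 11, repeated at Follow-up 2) | A list of assessments, referring to 3.2.2 | Cannot be determined |
| Dispensing 2 (3.2.4) | Toric fit (17), displacement and one-minute reading (18), lens fit (19), surface (20) | Yes |

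At Dispensing 2, no blacked-out text stands between 18e and 19, so the absence of a re-settle there is not a redaction effect. Toric fit at step 17 is read before the displacement and is unaffected.

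**What could reach the lens comparison.** Let a_A and a_B be the average shifts in a dispensing fit grade caused by the displacement for lenses A and B. Let n1 subjects have order AB and n2 have order BA, with N = n1 + n2.

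- If the test precedes grading at both dispensing visits, the A minus B difference shifts by a_A − a_B, whatever the split.
- If it does so only at Dispensing 2, order AB contributes −a_B and order BA contributes +a_A. The mean shift is (n2·a_A − n1·a_B)/N. At 25:25 this is (a_A − a_B)/2.

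In both cases a lens-specific part remains under perfect balance. It is zero at 25:25 only if a_A = a_B.

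**Size.** Residual rotation at one minute is 30 × (1 − r), where r is the share recovered. The documents give no r. Over an assumed range:

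- r = 0.33: about 20 degrees
- r = 0.50: 15 degrees
- r = 0.90: 3 degrees

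These are degrees of rotation. Centration and movement are graded from −2 to +2, and nothing in the documents converts one into the other. So a_A and a_B cannot be estimated and may be negligible.

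**Settling time.** Steps 14 to 16 allow three readings:

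- Step 14 is a leftover: 5 minutes, as at Dispensing 1.
- The lenses are applied a second time at step 15: 5 minutes from that application.
- Both settles are kept and the second application is ignored: 5 + 5 = 10 minutes.

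Only the third gives unequal times. It would be a period shift d, and the share reaching an unadjusted lens difference is |n1 − n2|/N: 0 at 25:25, 2/50 = 0.04 at 26:24, 6/50 = 0.12 at 28:22 and 10/50 = 0.20 at 30:20. These splits are illustrations; the visible text gives no allocation ratio.

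**The case against.** The strongest reply is that no harm is shown. The recovery range is assumed, and rotation is not centration, coverage or movement. The subject blinks normally for a minute before grading, and toric fit has already been recorded. Lens fit is also assessed at one week on lenses worn for at least two hours, and the dispensing reading may serve mainly to check that the lens can be issued. All of this stands as a limit on size. It does not justify the order, because the visible text does not say which visit supplies the outcome and nothing is gained by grading after the disturbance.

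Three stronger readings are tempting and are not supported:

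- A reader might infer from step 11 that the follow-ups use the opposite order. Step 11 is a list, not a sequence. It puts lens fit before toric fit, whereas the stepwise text at both dispensing visits puts toric fit first. It also defers to a section that is largely blacked out.
- A reader might infer that only the second period is disturbed. The blacked-out step 7 at Dispensing 1 occupies the same place as step 18 and may be the same test.
- A reader might infer that every subject has one lens read at five minutes and the other at ten. That requires ignoring the application in step 15. The numbering runs to 23 and then returns to 15 and 16, which suggests that steps were inserted and step 14 was left behind.

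**Conclusion.** The point holds in a limited form. At Dispensing 2 the plan grades lens fit and lens surface straight after a 30-degree manual displacement, with no written re-settle. If the lenses re-orient at different speeds, which the protocol's remark on stabilisation makes plausible but does not establish, the dispensing fit grades may carry a lens-dependent disturbance that randomised order does not remove.

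This is a weakness in measurement order, not a demonstrated bias. Its size is unknown, and it concerns the dispensing reading of a secondary outcome. Whether it extends to Dispensing 1 or the follow-ups cannot be judged from the visible text. The primary outcome, handling on removal, is untouched.

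The repeated application and settle in steps 14 to 16 is a minor and probably editorial fault. Any timing difference it caused would be a period effect that cancels between lenses when the sequences are balanced.

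**What to change.** 1. In section 3.2.4, move steps 19 and 20 ahead of step 18, so that rotational recovery is the last on-eye lens assessment. State the same order for the initial visit, Dispensing 1 and both follow-ups. Where the blacked-out text already has it, only confirmation is needed.
2. Reconcile steps 14 to 16 with Dispensing 1, which has one application by the subject and one five-minute settle, and correct the step numbers at the end of the section.
3. Name in section 1.4 the visit that supplies the secondary lens-fit outcome, if the blacked-out text does not already do so.

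The cost is an edit to the protocol and the case report form. No procedure, visit or subject is added.

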3.2.5 Follow-up 2 visit

Subjects should attend wearing the study lenses which should have been in situ for at least two hours. Subjects who attend without lenses in situ for at least two hours will usually be rescheduled.

1. The same procedures as at Follow-up 1 (Section 3.2.4 above) will be carried out.
2. [REDACTED]
3. At the final visit (or when the subject is discontinued at an earlier visit) arrangements to issue the subject with their payment will be made, although they may have been asked by the investigator to attend a post-study follow-up visit. They should continue to use their lenses and solutions as advised, and seek aftercare for their contact lenses.

3.2.6 Post-study follow-up visit

In the case of a subject who exits the study with significant clinical signs or symptoms, the investigator must undertake to examine the subject at intervals he/she determines to be clinically appropriate until the sign or symptom has resolved or returned to a level that is considered to be clinically acceptable. Details from these visits will be recorded on a post-study follow-up visit form.

3.3 Monitoring subject compliance

Subjects are required to adhere to the instructions provided during this clinical investigation. This will be confirmed at the study visit(s) by verbal questioning of the subject by the investigator.

3.4 Missing, unused and spurious data

The absence of any data will be carefully and critically considered. If appropriate, partial datasets will be included in the final analysis. Any data missing from a subject visit will be outlined in the report by indicating the number of subjects included for each analysis. Data that are unused or considered to be spurious will be detailed and discussed in the report.

Section 4. Study co-ordination

4.1 Document processing

All case report forms will be processed and evaluated by Eurolens Research, who will produce the final report with full statistical analysis. A draft report will be sent to the Sponsor Contact Person in order to make comments and ask for re-drafts. If no comments are received from the Sponsor Contact Person within eight weeks, a final report will be released with a separate document control page (in duplicate), requesting the Sponsor Contact Person to sign both copies, one to keep and the other to be returned to Eurolens Research.

4.2 Disclosure

All matters relating to this clinical study are confidential and should only be disclosed to relevant authorised parties. More precise details relating to disclosure are outlined in the Research Agreement. None of the investigators involved in this work owns equity in the funding company.

4.3 Personnel

A series of horizontal black bars of varying lengths, representing a redacted list of personnel names.

Protocol amendment

[figure not shown]
Study title: The comparative clinical performance of two daily disposable toric contact lenses

The table below lists the changes to be implemented in this work:

New revision no.	Section/s to be Amended and details																											
1	
Both lenses are now available in all axes from 10 to 180 (10 degree steps)
 
Section 2.6.1 Lenses
 
Table 2: Study lenses now amended to reflect the change of study lenses.
 
  
 Name	MMDay toric	DAILIES Total1 for Astigmatism	
   
 Manufacturer	CooperVision Inc	Alcon	
 
 Material	Silafilcon A	Delefilcon A	
 
 EWC (%)	54%	Core water content 33%, surface water content >80%	
 
 BOZR (mm)	8.6	8.6	
 
 Diameter (mm)	14.5	14.5	
 
 Spherical powers (DS)	Plano to -6.00D	Plano to -6.00D	
 
 Cylinder powers (DC)	-0.75, -1.25, -1.75	-0.75, -1.25, -1.75	
 
 Axes (degrees)	10-180, 10 degree steps	10-180, 10 degree steps	
  
 
Table 1: Study lenses
	Name	MMDay toric	DAILIES Total1 for Astigmatism	Manufacturer	CooperVision Inc	Alcon	Material	Silafilcon A	Delefilcon A	EWC (%)	54%	Core water content 33%, surface water content >80%	BOZR (mm)	8.6	8.6	Diameter (mm)	14.5	14.5	Spherical powers (DS)	Plano to -6.00D	Plano to -6.00D	Cylinder powers (DC)	-0.75, -1.25, -1.75	-0.75, -1.25, -1.75	Axes (degrees)	10-180, 10 degree steps	10-180, 10 degree steps
Name	MMDay toric	DAILIES Total1 for Astigmatism																										
Manufacturer	CooperVision Inc	Alcon																										
Material	Silafilcon A	Delefilcon A																										
EWC (%)	54%	Core water content 33%, surface water content >80%																										
BOZR (mm)	8.6	8.6																										
Diameter (mm)	14.5	14.5																										
Spherical powers (DS)	Plano to -6.00D	Plano to -6.00D																										
Cylinder powers (DC)	-0.75, -1.25, -1.75	-0.75, -1.25, -1.75																										
Axes (degrees)	10-180, 10 degree steps	10-180, 10 degree steps																										
2	
Number of subjects
 
The original protocol stated that up to 55 subjects should be enrolled, as the power calculation is based on 50 subjects completing the study.
 
As a result of a much higher number of ineligible subjects than expected, up to 65 subjects will now be enrolled. The intended number of subjects to complete remains 50.
 
As the lens SKU range is now increased, any subject who was originally ineligible owing to the required lens not being available, can now be re-enrolled and, if they wish to re-enrol, will be treated as a new subject (i.e. they will reconsent and re-attend the initial visit and so on).
 
Subjects found ineligible for other reasons will not be re-enrolled.
																											

Table 2: Changes to protocol C20-691 (version 1.0)

Document approved by:

Protocol amendment

Study title: The comparative clinical performance of two daily disposable toric contact lenses

The table below lists the changes to be implemented in this work:

New revision no.	Section/s to be Amended and details
1	
Inclusion criterion 1 originally read 'They are aged between 18 and 40 years old and have capacity to volunteer'.
 
Now amended to 'They are at least 18 years old and have capacity to volunteer'

2	
Number of subjects
 
The original protocol stated that up to 55 subjects should be enrolled, as the power calculation is based on 50 subjects completing the study. Protocol amendment 1 increased the maximum number to 65. In order to avoid falling short of the required number of completed subjects, owing to a high rate of subjects being found ineligible at the initial visit, the maximum number of subjects to be enrolled is increased to 70.

Table 1: Changes to protocol C20-691 (version 1.0)

Document approved by:
